13.3.2 Global Response Score

The individual component scores for skin, nodes, blood, and viscera are incorporated into the definition of the Global Response Score (see table below).

| Global Score | Definition | Skin | Nodes | Blood | Viscera |
|--------------------------|---|-------------|--|--------------|----------------|
| Complete Response (CR) | Complete disappearance of all clinical evidence of disease | CR | All categories have CR/noninvolved (NI) | | |
| Partial Response (PR) | Regression of measurable disease | CR | All categories do not have a CR/NI and no category has a PD | | |
| | | PR | No category has a PD and if any category involved at baseline, at least one has a CR or PR | | |
| Stable Disease (SD) | Failure to attain CR, PR, or PD representative of all disease | PR | No category has a PD and if any category involved at baseline, no CR or PR in any | | |
| | | SD | CR/NI, PR, SD in any category and no category has a PD | | |
| Progressive Disease (PD) | Progressive disease | | PD in any category | | |
| Relapse | Recurrence disease in prior CR | | Relapse in any category | | |

References:

Olsen EA, S Whittaker, Kim YH, Duvic M, Prince HM, Lessin SR, et al. Clinical end points and response criteria in mycosis fungoides and Sézary Syndrome: a consensus statement of the International Society for Cutaneous Lymphomas, the United States Cutaneous Lymphoma Consortium, and the Cutaneous Lymphoma Task Force of the European Organisation for Research and Treatment of Cancer. *J Clin Oncol* 2011; 29(18):2598-2607.

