4.2.1 Inclusion Criteria

1. Male or female age 18 years or older.
2. Refractory or relapsed lymphoma (per WHO Classification system) defined as:
 - Non-Hodgkin lymphoma (NHL): Patients with histologically confirmed NHL (including stage \geq Ib cutaneous T-cell lymphoma [CTCL]) who have failed or are intolerant to any established therapy known to provide clinical benefit at current state of disease. There is no upper limit to the number of prior therapies.
 - Hodgkin lymphoma: Patients with histologically confirmed classical Hodgkin lymphoma who have failed or are intolerant to brentuximab vedotin. Patients must have received a checkpoint inhibitor. There is no upper limit to the number of prior therapies.
3. Pathologically confirmed relapsed or refractory lymphoma; a biopsy at any relapse is acceptable.
4. Availability of formalin-fixed paraffin-embedded (FFPE) tumor tissue block. An FFPE block from a current biopsy is preferred; however, archival tissue taken at any prior relapse is acceptable. If tissue block is not available, slides from a FFPE block may be acceptable for eligibility upon consultation with the Sponsor.
5. Measurable disease, defined by the 2014 Lugano Classification Criteria (including CTCL patients without evidence of skin disease) ([Appendix 13.2](#)). CTCL patients with skin disease and modified Severity-Weighted Assessment Tool (mSWAT) criteria >0 , or absolute Sézary count ≥ 1000 cells/ μ L are eligible ([Appendix 13.3](#)).
6. ECOG performance status 0 to 2.
7. Absolute neutrophil count (ANC) ≥ 1500 / μ L. Criterion not applicable to adult T cell leukemia/lymphoma (ATLL) patients.
8. Platelet count of ≥ 75000 / μ L. Criterion not applicable to ATLL patients.
9. Hemoglobin ≥ 9.0 g/dL without transfusion within the 2 weeks prior to Day 1. Criterion not applicable to ATLL patients.
10. Serum/plasma creatinine ≤ 1.5 mg/dL, or if the patient has a creatinine > 1.5 mg/dL, a measured creatinine clearance must be > 80 mL/min as calculated by the Cockcroft and Gault equation.⁴

11. Serum/plasma alkaline phosphatase, alanine aminotransferase, and aspartate aminotransferase ≤ 2 times the upper limit of normal (ULN); ≤ 5 times ULN if there is liver or bone involvement.
12. Total serum/plasma bilirubin ≤ 1.5 times ULN (patients with known Gilbert's syndrome may have a total bilirubin up to ≤ 3 times ULN).

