13.3.1.4 Response Definitions

Responses will be determined by the criteria described in the table below. Progression of disease while on treatment should be confirmed by a second assessment 1 to 4 weeks later so that patients who experience a temporary flare of disease due to skin infection or other intercurrent illnesses are not removed from the study prematurely.

| Response | Description |
|---|--|
| Skin | |
| Complete Response (CR) | No evidence of disease; 100% clearance of skin lesions. |
| Partial Response (PR) | ≥50% decrease in skin scores compared to baseline and improvement is maintained for a minimum of 4 weeks |
| Stable Disease (SD) | < 50% decrease in skin scores compared to baseline |
| Progressive Disease (PD) | ≥ 25% increase in skin scores compared to baseline while the patient is actively taking the study drug, or new tumor(s) ≥ 1 cm diameter in skin disease only patient, or ≥ 50% increase in the sum of the products of the greatest diameters of pathologically positive lymph nodes (should be documented by biopsy) compared to baseline while the patient is actively taking the study drug. |
| Relapse | Any disease recurrence in those with complete response. |
| Lymph Nodes (peripheral and central) | |
| CR | All lymph nodes are now ≤ 1.5 cm in greatest transverse (long axis) diameter by method used to assess lymph nodes at baseline or biopsy negative for lymphoma; in addition, lymph nodes that were N ₃ classification and ≤ 1.5 cm in their long axis and > 1 cm in their short axis at baseline, must now be ≤ 1 cm in their short axis or biopsy negative for lymphoma |
| PR | Cumulative reduction > 50% of the SPD of each abnormal lymph node at baseline and no new lymph node > 1.5 cm in the diameter of the long axis or >1.0 cm in the diameter of the short axis if the long axis is 1-1.5 cm diameter |
| SD | Fails to attain criteria for CR, PR, or PD |
| PD | ≥ 50% increase in SPD from baseline of lymph nodes or Any new node > 1.5 cm in the long axis or > 1 cm in the short axis if 1-1.5 cm in the long axis that is proven to be N ₃ histologically or Loss of response: > 50% increase from nadir in SPD of lymph nodes in those with PR |
| Relapse | Any new lymph node > 1.5 cm in the long axis in those with CR proven to be N ₃ histologically. |
| Viscera | |

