#### **4.9 Efficacy Analyses**

Disease assessment will be performed according to protocol. The endpoints described in this section use the investigator's evaluation according to the Lugano Classification criteria or Global Response Score Grading Scales for CTCL patients and clinical progression from End of Treatment (EOT)/Study disposition page.

Tumor assessment data (target lesions, non-target lesions, and new lesions, overall response, SUV max, Deauville score, etc.) for non-CTCL patients, and modified Severity-Weighted Assessment Tool (mSWAT) scores for CTCL patients will be listed. A separate listing will contain derived data for DOR, PFS, and OS.

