#### **4.9.1 Overall Response Rate**

Overall response rate is defined as the proportion of patients who achieve either CR or PR as best overall response as assessed by investigators according to the Lugano Classification criteria or Global Response Score Grading Scales for CTCL patients before the start of subsequent anticancer therapy or procedure.

The order of overall response category is: CR, PR, SD, NE, PD (including disease recurrence/relapse). The overall response category will be derived based on response assessment performed on or before the start of subsequent anticancer therapy/procedure. Patients without documented subsequent anticancer therapy and/or with missing start date of anticancer therapy will be considered as not having received subsequent anticancer therapy. If a patient only has one valid disease assessment which is SD, and the assessment is within 35 days after the first dose, the overall response for this patient will be considered as NE.

The overall response rate and the corresponding 95% two-sided exact confidence interval at each dose level will be presented. Subgroup analysis may be provided if relevant.

Percent change from baseline in the sum of product of diameters (SPD) for target lesions for non-CTCL patients and mSWAT total score for CICL patients will be presented for available data in the efficacy analysis set by dose level. These data will also be displayed as a waterfall plot, with vertical bars representing the sorted values of best percent reduction for each patient.

Tumor response and lesion measurement (or mSWAT) will be listed by assessment visit.

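### CTCL patients without skin disease are eligible, but the Global Response Score has no entry for uninvolved skin, so their response and their mSWAT percent change are undefined as written

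*Protocol*

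**What the plan says.** **Eligibility.** Protocol 4.2.1, inclusion 5 (and the synopsis), accepts disease measurable by Lugano 2014, "including CTCL patients without evidence of skin disease". In 4.2.1 that sentence cross-refers to Appendix 13.2 (Lugano). The next sentence, on CTCL with skin disease and a positive mSWAT or a Sézary count, cross-refers to Appendix 13.3.

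**Scoring.** Protocol 7.1 bases response on Lugano and, for CTCL, on the Global Response Score. SAP 4.9.1 defines ORR by CR or PR "as assessed by investigators according to the Lugano Classification criteria or Global Response Score Grading Scales for CTCL patients". Neither makes an exception for CTCL without skin disease.

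**The table.** In Protocol 13.3.2 the CR, PR and SD rows each start from a skin result of CR, PR or SD. The noninvolved code is offered for nodes, blood and viscera only. Only the PD and Relapse rows leave skin open. With skin in CR, global PR needs only this of the other compartments: "All categories do not have a CR/NI and no category has a PD". The definition column for global PR reads "Regression of measurable disease".

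**Skin definitions.** Protocol 13.3.1.4 defines skin CR as "No evidence of disease; 100% clearance of skin lesions". Skin PR, skin SD and the score-based part of skin PD are percent changes from the baseline skin score. There is no uninvolved category.

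**Displays.** SAP 4.9 says "modified Severity-Weighted Assessment Tool (mSWAT) scores for CTCL patients will be listed". SAP 4.9.1 assigns percent change in SPD to non-CTCL patients and percent change in mSWAT to CTCL patients, and draws the waterfall plot from these.

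**The concern.** The protocol names a group as eligible and then sends it to a response table that cannot take it. Each site must choose a code for clear skin, and the choice, not the disease, can decide whether the patient is a responder.

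Three things depend on it. ORR can move up or down. A patient wrongly coded PR enters the DOR analysis (SAP 4.9.2). In Part 1, the cap of 10 patients at a dose level can be exceeded only if at least 3 of the 10 have PR or better (Protocol 4.1.1), so response coding may inform an enrolment decision as well as a table. Separately, the waterfall plot uses for these patients a measure that has no value at their baseline.

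**Working it through.** The documents give no figure to reproduce for this point, so the check applies the table in 13.3.2 as rules.

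**Test case.** CTCL with nodal disease only: blood and viscera noninvolved (NI), skin never involved. The code given to skin is varied. The first PR row is read as meaning that not all other categories are CR/NI.

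| Nodes | Skin coded CR | Skin coded SD | Skin coded NI |
|---|---|---|---|
| CR | CR | SD | no row |
| PR | PR | SD | no row |
| SD | **PR** | SD | no row |
| PD | PD | PD | PD |

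Coding skin as CR gives the expected answer for nodal CR, PR and PD but turns stable nodes into a global PR. Coding skin as SD makes any nodal response, even a complete one, a global SD. Coding skin as NI leaves every non-progressing patient without a category. No single code gives a sensible result in all four rows.

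**The ambiguous phrase.** The first PR row could instead mean that none of the other categories is CR/NI. In the test case, skin CR with nodes SD or PR then fits no row, because blood and viscera are NI. That reading also fails ordinary patients: skin disease that clears completely, with stable nodes and uninvolved blood and viscera, would have no category either. Reading it as not all is therefore the workable sense. If nodes, blood and viscera are all involved and all SD, both readings give PR with skin coded CR.

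**mSWAT.** The 12 regional percentages in 13.3.1.3 are 7 + 2 + 13 + 13 + 5 + 1 + 8 + 6 + 5 + 19 + 14 + 7 = 100. The maximum score is 100 × 4 = 400, which matches the stated scale of 0 to 400; no lesions gives 0. Percent change = 100 × (follow-up − baseline) / baseline. With baseline 0 this is 0/0 if the skin stays clear and has a zero denominator if lesions appear, so it is undefined. Absolute change is defined.

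**Scale.** The number of such patients is not given. As an illustration, take a cohort of 10 (Protocol 8.3 plans Part 2 cohorts of about that size) in which one patient moves from PR to SD. The exact two-sided 95% limits are Beta(0.025; x, n − x + 1) and Beta(0.975; x + 1, n − x):

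- 3/10 = 30%, interval 6.7% to 65.2%
- 2/10 = 20%, interval 2.5% to 55.6%

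The change is 1/10 = 10 points. In a Part 1 group of 10 it is also the step between meeting and missing 3 of 10.

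**The case against.** The strongest objection is that a literal reading does not give PR. A reader might infer that the protocol states a rule turning stable nodal disease into PR, so that every such patient who has not progressed is a responder. It does not. Strictly, a patient with uninvolved skin fits no CR, PR or SD row. PR requires a site to code never-involved skin as CR, and the second half of the skin CR definition presupposes lesions that have cleared. A global PR with stable nodes also contradicts the table's own requirement of regression. This stands: the defect is a missing rule, and PR is one of its possible results.

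Second, inclusion 5 points these patients to Appendix 13.2, so Lugano scoring is a natural route. Under Lugano, less than a 50% fall in SPD without progression is SD. This stands in part. The cross-reference concerns measurability, and no section says that response in these patients follows Lugano. SAP 4.9.1 divides patients only into CTCL and non-CTCL.

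Third, the consequences can be overstated:

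- The 3-of-10 rule is not mechanical. Expansion is at the steering committee's option, other appropriate response measures are allowed, and the committee's medical judgment prevails over the model.
- Nodal data are not necessarily lost. SAP 4.9.1 presents percent change for available data and lists lesion measurements or mSWAT by visit. The clear loss is a bar in the waterfall plot.
- A reader might extend the point to patients who qualify on a Sézary count alone. The wording of inclusion 5 can be read as requiring skin disease there too, so the point rests on the skin-free group that is named outright.

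Finally, ORR is secondary, and SAP section 4 plans no hypothesis tests. That limits the weight of the point but does not supply the missing rule.

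**Conclusion.** The concern holds as a gap in the response rules. For CTCL patients without skin disease, the Global Response Score is undefined as written for every outcome except progression or relapse. Whichever code a site adopts, some outcomes are wrong or absent: stable nodes become PR, a nodal response becomes SD, or there is no category. Percent change in mSWAT is undefined for them, and the SAP gives their nodal change no place in the waterfall plot.

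The effect on ORR is 10 points per patient in a cohort of 10, in either direction. That is simply the weight of one patient, not an estimate of bias; the actual effect is unknown because the subgroup size is not stated and may be small. The conclusion assumes that the Global Response Score applies to all CTCL patients, as Protocol 7.1 and SAP 4.9.1 say without exception. If the intention was Lugano, the ambiguity in scoring goes once that is written down, but the waterfall problem remains.

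**What to change.** In Protocol 13.3.2 and SAP 4.9, state that when skin is uninvolved at baseline (mSWAT = 0), skin is scored NI and the global CR, PR or SD is taken from the involved compartments only:

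- CR if all involved compartments are CR
- PR if none is PD and at least one, but not every one, is CR, or at least one is PR
- SD otherwise, if none is PD

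With this rule the nodal-only test case gives CR, PR and SD for nodal CR, PR and SD. Alternatively, state that these patients are scored by Lugano, in line with the Appendix 13.2 cross-reference in inclusion 5. Either will do, provided one is written down and used at all sites.

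In SAP 4.9 and 4.9.1, use SPD percent change in the waterfall plot and listing for CTCL patients with baseline mSWAT = 0.

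The score-based skin PD criterion also has no value at baseline 0. How new skin lesions are handled in these patients should be reconciled with the skin PD and confirmation wording in 13.3.1.4, without adding a new progression rule here.

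The cost is one table row and a few SAP sentences, with no new assessments. One or two nominal responders might be lost if such patients were enrolled and had been scored with skin as CR.

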13.4 Appendix: CTCAE Immune System Hypersensitivity Grades

| Adverse Event | Grade 1 | Grade 2 | Grade 3 | Grade 4 | Grade 5 |
|---|--|---|---|--|---------|
| Allergic reaction | Transient flushing or rash, drug fever <38°C (<100.4°F); intervention not indicated | Intervention or infusion interruption indicated; responds promptly to symptomatic treatment (e.g., antihistamines, NSAIDs, narcotics); prophylactic medications indicated for ≤24 hours | Prolonged (e.g., not rapidly responsive to symptomatic medication and/or brief interruption of infusion); recurrence of symptoms following initial improvement; hospitalization indicated for clinical sequelae (e.g., renal impairment, pulmonary infiltrates) | Life-threatening consequences; urgent intervention indicated | Death |
| Definition: A disorder characterized by an adverse local or general response from exposure to an allergen. | | | | | |
| Anaphylaxis | - | - | Symptomatic bronchospasm, with or without urticaria; parenteral intervention indicated; allergy-related edema/angioedema; hypotension | Life-threatening consequences; urgent intervention indicated | Death |
| Definition: A disorder characterized by an acute inflammatory reaction resulting from the release of histamine and histamine-like substances from mast cells, causing a hypersensitivity immune response. Clinically, it presents with breathing difficulty, dizziness, hypotension, cyanosis, and loss of consciousness and may lead to death. | | | | | |
| Autoimmune disorder | Asymptomatic; serologic or other evidence of autoimmune reaction, with normal organ function; intervention not indicated | Evidence of autoimmune reaction involving a non-essential organ or function (e.g., hypothyroidism) | Autoimmune reactions involving major organ (e.g., colitis, anemia, myocarditis, kidney) | Life-threatening consequences; urgent intervention indicated | Death |

| Adverse Event | Grade 1 | Grade 2 | Grade 3 | Grade 4 | Grade 5 |
|---|--|---|---|---|---------|
| Definition: A disorder resulting from loss of function or tissue destruction of an organ or multiple organs, arising from humoral or cellular immune responses of the individual to his own tissue constituents. | | | | | |
| Cytokine release syndrome | Mild reaction; infusion interruption not indicated; intervention not indicated | Therapy or infusion interruption indicated but responds promptly to symptomatic treatment (e.g., antihistamines, NSAIDs, narcotics, intravenous fluids); prophylactic medications indicated for ≤ 24 hours | Prolonged (e.g., not rapidly responsive to symptomatic medication and/or brief interruption of infusion); recurrence of symptoms following initial improvement; hospitalization indicated for clinical sequelae (e.g., renal impairment, pulmonary infiltrates) | Life-threatening consequences; pressor or ventilatory support indicated | Death |
| Definition: A disorder characterized by nausea, headache, tachycardia, hypotension, rash, and shortness of breath; it is caused by the release of cytokines from the cells. | | | | | |
| Serum sickness | Asymptomatic; clinical or diagnostic observations only; intervention not indicated | Moderate arthralgia; fever, rash, urticaria, antihistamines indicated | Severe arthralgia or arthritis; extensive rash; steroids or intravenous fluids indicated | Life-threatening consequences; pressor or ventilatory support indicated | Death |
| Definition: A disorder characterized by a delayed-type hypersensitivity reaction to foreign proteins derived from an animal serum. It occurs approximately 66 to 21 days following the administration of the foreign antigen. Symptoms include fever, arthralgias, myalgias, skin eruptions, lymphadenopathy, chest marked discomfort, and dyspnea. | | | | | |

| Adverse Event | Grade 1 | Grade 2 | Grade 3 | Grade 4 | Grade 5 |
|---|---|---|--|--|----------------|
| Immune system disorders - Other, specify | Asymptomatic or mild symptoms; clinical or diagnostic observations only; intervention not indicated | Moderate; minimal, local or noninvasive intervention indicated; limiting age-appropriate instrumental ADL | Severe or medically significant but not immediately life-threatening; hospitalization or prolongation of existing hospitalization indicated; disabling; limiting self-care ADL | Life-threatening consequences; urgent intervention indicated | Death |

Abbreviations: ADL, Activities of daily living; NSAIDs, non-steroidal anti-inflammatory drugs.
 Adapted from CTCAE 4.0 – June 14, 2010, Immune system disorders.

13.5 Appendix: Dose Escalation Scheme Report

13.5.1 Overview

A primary objective of the dose escalation portion of the study is to estimate an MTD. The MTD will be the highest safe dose that has at least a 60% probability that the dose limiting toxicity (DLT) rate is < 30%. The DLT observation period is 1 cycle.

Dose escalation will begin with the 3 µg/kg starting dose (Dose Level 1). There will be 33 dose levels including all dose levels from:

- 0.003 to 0.02 mg/kg in increments of 0.001
- 0.02 to 0.05 mg/kg in increments of 0.005
- 0.05 to 0.10 mg/kg in increments of 0.01
- 0.10 to 0.30 mg/kg in increments of 0.05

Dose escalation will be conducted according to a continual reassessment method (CRM). Non-DLT toxicity events (i.e. Grade 2 or higher toxicities) will inform the probability of DLT at each dose level. Dose escalation is also conducted according to a set of rules that govern entry into the study and assignment of dose level. These rules allow that untried dose levels may be skipped. The trial is continuously monitored for safety and early stopping for successfully identifying the MTD.

13.5.2 Continual Reassessment Method

Dose escalation in this study will be conducted using the CRM. For each dose, $d = 1, \dots, 33$, we model the ordinal outcome of no toxicity event, non-DLT (i.e. Grade 2) toxicity event, or a DLT.

We model the log odds of a DLT,

$$\theta_d = \log\left(\frac{\pi_{DLT}}{1 - \pi_{DLT}}\right)$$

with a two-parameter model

$$\theta_d = \alpha + \beta d$$

We model the log odd-odds of a non-DLT toxicity

$$\rho_d = \log\left(\frac{\pi_{grade2}}{1 - \pi_{grade2}}\right)$$

as related to DLTs by including an additive term, γ , which must be > 0 ,

$$\rho_d = (\alpha + \gamma) + \beta d.$$

We place the following independent prior distributions on the parameters.

$$\alpha \sim N(-3, 6^2)$$

$$\beta \sim N(8, 20^2)$$

$$\gamma \sim N^+(3, 6^2)$$

This parameterization imposes that Grade 2 or higher toxicities (which include DLTs) will occur more frequently than DLTs. We use “pseudo-prior” weighting to impose a prior expectation of the rate of DLTs that helps shape the correlation of the parameters. We assume one observation each of three doses. We place one observation with 0% DLT on the 0.003 mg/kg dose, with 30% DLT on the on the 0.10 mg/kg dose, and with 60% DLT on the 0.20 mg/kg dose.

After each patient is treated and assessed for non-DLT toxicity or DLT, the distributions of all parameters are updated and the MTD is estimated based on the posterior probability of DLT at each dose.

Additionally, we define a dose as safe if there is at least a 60% probability that the DLT rate is $< 30\%$,

$$\Pr(\pi_d < 30\%) > 60\%.$$

Patients cannot be assigned to a dose that is not safe by this definition.

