7.3.1 Dose-Limiting Toxicities and Dose-Escalation Scheme

7.3.1.1 Definition of Dose-Limiting Toxicities

A DLT is defined as any of the following events, except those that are clearly due to underlying disease or extraneous causes:

- A hematologic DLT is defined as (not applicable for ATLL patients):
 - Grade 3 or 4 febrile neutropenia or neutropenic infection.
 - Grade 4 neutropenia lasting > 7 days.
 - Grade 4 thrombocytopenia.
 - Grade 3 thrombocytopenia with clinically significant bleeding, or Grade 3 thrombocytopenia requiring a platelet transfusion.
 - Grade 4 anemia.
- For ATLL patients, a hematologic DLT is defined as:
 - Any Grade 4 neutropenia lasting \geq 42 days from the start of the cycle in the absence of evidence of residual leukemia.
 - Grade 3 or higher event of thrombocytopenia or a Grade 4 anemia, with a hypocellular bone marrow lasting for \geq 42 days from the start of the cycle, in the absence of evidence of residual leukemia (i.e., with <5% malignant cells).
- A non-hematologic DLT is defined as:
 - Grade 4 tumor lysis syndrome (Grade 3 TLS will not constitute DLT unless it leads to irreversible end-organ damage).
 - Grade 3 or higher (including nausea, vomiting, diarrhea, and electrolyte imbalances lasting \geq 48 hours despite optimal therapy [excluding all grades of alopecia]).
 - Grade 3 or higher hypersensitivity reaction (regardless of premedication) ([Appendix 13.4](#)).
 - Skin ulceration \geq Grade 2.
 - Peripheral sensory or motor neuropathy \geq Grade 2.

Note: The DLT period for dose escalation will be 1 cycle; however, the adaptive dose-escalation algorithm will incorporate cumulative DLTs occurring through Cycle 3.

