13.5.4.1 Safety Monitoring

The lowest dose (0.003 mg/kg) will be considered unsafe if it has a probability $< 25\%$ of a DLT rate $< 30\%$. The trial will stop, and no MTD found, if the lowest dose is considered unsafe (hence all doses are considered unsafe).

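### The CRM slope prior is not held positive, so the printed model does not guarantee the rising DLT curve that the lowest-dose stopping rule and the MTD definition rely on

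*Protocol*

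**What the plan says.** Protocol 13.5.2 models the log odds of a DLT as alpha + beta × d. Under the sentence "We place the following independent prior distributions on the parameters" it sets alpha ~ N(-3, 6^2), beta ~ N(8, 20^2) and gamma ~ N+(3, 6^2). The only sign constraint is on gamma, which enters "by including an additive term, γ , which must be > 0". The ordering that this secures is between toxicity grades: "This parameterization imposes that Grade 2 or higher toxicities (which include DLTs) will occur more frequently than DLTs". Nothing in the protocol or SAP orders the DLT rate by dose.

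Three pseudo-observations then shape the prior: "We place one observation with 0% DLT on the 0.003 mg/kg dose, with 30% DLT on the on the 0.10 mg/kg dose", and 60% on 0.20 mg/kg.

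Two rules use the fitted curve:
- A dose is safe if Pr(DLT rate < 30%) exceeds 60% (13.5.2), and by 13.5.1 "The MTD will be the highest safe dose that has at least a 60% probability".
- The lowest dose is unsafe if that probability falls below 25%. Section 13.5.4.1 then says: "The trial will stop, and no MTD found, if the lowest dose is considered unsafe (hence all doses are considered unsafe").

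Two provisions let DLTs accrue below the current dose. Sections 4.1.1 and 7.3.1.2 allow added enrolment at lower doses, and by 7.3.1.1 "the adaptive dose-escalation algorithm will incorporate cumulative DLTs occurring through Cycle 3".

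**The concern.** If the lowest dose is unsafe, it follows that all doses are unsafe only when the DLT rate cannot fall as dose rises. Taking the highest passing dose as the MTD makes the same assumption. A slope free to be negative does not honour it. DLTs at a low dose can then be explained in two ways: the drug is toxic everywhere, or toxicity declines with dose. The second explanation raises the calculated safety of high, untried doses. If DLT-free patients at higher doses also support it, an extra DLT could move the MTD estimate upwards. The MTD is a primary objective of Part 1.

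**Working it through.** **Inputs.** The priors, pseudo-observations and 60% rule are from 13.5.2, the 25% limit from 13.5.4.1, and the dose levels from 13.5.1.

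**The plan's own figures.** The level count reproduces: 18 + 6 + 5 + 4 = 33. The 61% early-stop and 37% lowest-dose selection probabilities in 13.5.5.7 cannot be checked, because the true curve and the maximum N used are not in the text. Assumed flat DLT rates of 40%, 50% and 60% (150 trials each, maximum N 40) gave stopping in 61%, 88% and 99% and lowest-dose selection in 2%, 3% and 0%. The pair is not matched, which is not evidence of an error.

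**Dose scale (assumption).** Section 13.5.2 indexes doses 1 to 33. At the prior means, index 1 gives logit -3 + 8 = 5, a DLT rate of 99.3%. In mg/kg the rates are 4.9% at 0.003 (logit -2.976), 10.0% at 0.10 (logit -2.2) and 35.4% at 0.30 (logit -0.6). I take d in mg/kg.

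**Step 1, prior slope.** P(beta < 0) = Phi((0 - 8)/20) = Phi(-0.4) = 34.5%, whatever the dose scale.

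**Step 2, posterior.** On a grid over (alpha, beta), DLT data only, each patient contributes π^y (1 - π)^(1-y) with logit π = alpha + beta × d. The pseudo-observations enter with y = 0, 0.3 and 0.6. Safety at dose d is S(d) = Pr(alpha + beta × d < log(0.3/0.7) = -0.847). With the pseudo-observations alone, P(beta < 0) is about 12%.

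**Step 3, lowest-dose stop.** After 3 DLTs in 4 patients at 0.003:

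| Slope | S(0.003) | S(0.30) |
|---|---|---|
| as printed | 0.13 | 0.32 |
| beta > 0 | 0.19 | 0.01 |

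As printed, the untried top dose is rated safer than the dose that produced the DLTs. Before any data S(0.30) was 0.20. Over every DLT count in 1 to 10 patients at 0.003, however, whenever the stop fires no dose exceeds 0.42, so none reaches 60%.

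**Step 4, MTD.** Take 3 DLT-free patients at each of 0.003, 0.006, 0.012, 0.02, 0.04, 0.06, 0.08, 0.10 and 0.15, then add 2 patients with DLTs at 0.02:

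| Slope | Data | P(beta<0) | S(0.20) | S(0.25) | MTD |
|---|---|---|---|---|---|
| as printed | before | 0.06 | 0.68 | 0.46 | 0.20 |
| as printed | after | 0.33 | 0.77 | 0.66 | 0.25 |
| beta > 0 | before | 0 | 0.66 | 0.42 | 0.20 |
| beta > 0 | after | 0 | 0.65 | 0.50 | 0.20 |

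The full ordinal model with gamma, and no Grade 2 events in the DLT-free patients, moves from 0.20 to 0.30 as printed and stays at 0.20 with beta > 0. If instead one of every three such patients has a Grade 2 event, the MTD is already at the 0.30 ceiling and cannot rise. The size therefore depends on the Grade 2 data.

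**Step 5, ordinary data.** In 400 simulated trials on each of three assumed rising curves, the MTD quantiles with and without the restriction were almost the same. In 1,200 free-slope trials without lower-dose expansion or late DLTs, no DLT raised the MTD.

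**Step 6, what the restriction costs.** With 3 DLTs in 5 patients at 0.003, S(0.003) is 0.21 as printed (stop) and 0.28 with beta > 0 (no stop), DLT data only. At an assumed flat 40% DLT rate, stopping was 61% free against 52% restricted, with a standard error of about sqrt(0.61 × 0.39/150) = 4 points.

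**The case against.** The best reply is that the flaw hardly reaches a patient.

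- When the lowest-dose stop fires on 0.003 mg/kg data, no dose is safe and the trial stops as written. A reader might infer from S(0.30) = 0.32 that the top dose clears the 25% limit. That limit is written for the lowest dose only; other doses must pass 60%. This stands.
- The caps in 13.5.3.2 limit assignment. After a DLT the step is at most 50%, so from 0.15 the ceiling is 0.225 and the highest available level is 0.20. Early stopping for success needs at least 3 complete patients at the MTD (13.5.4.2). Under 7.3.1.2 the committee's medical judgment prevails over the CRM, but it cannot go above the CRM dose. All this stands for assignment. It does not correct the MTD estimate, and the 3-patient condition is attached to early stopping only.
- A reader might infer that low-dose DLTs below a clean escalation are a likely interim state. The protocol permits them, through lower-dose expansion or late-cycle counting, but neither route was simulated and no frequency can be claimed. With DLTs at 0.003 and nothing higher, the MTD falls: 0.10 before data, 0.045 after 1 of 2, none after 2 of 2.
- The free slope is not uniformly less cautious: it stops somewhat more readily at the lowest dose. This stands and belongs among the costs of the change.

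**Conclusion.** The point holds in a limited form. As printed, 13.5.2 allows a falling DLT curve with 34.5% prior probability, about 12% after the pseudo-observations. The inference in 13.5.4.1 and the MTD definition are therefore not guaranteed by the model. On lowest-dose data alone this is a defect of logic without practical effect. For ordinary rising data it is small. It matters where DLTs surface at low doses beneath DLT-free higher doses: the model MTD can then rise after added DLTs, by one level (0.20 to 0.25 mg/kg) in the DLT-only example.

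The posterior figures assume dose in mg/kg and pseudo-observations entered as one fractional observation each; the 34.5% needs neither. The documents do not show that the software left the slope free, that the printed operating characteristics are wrong, or that patients would be assigned to the top dose after low-dose DLTs. The change is worth making because it is specific and cheap, not because harm has been shown.

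**What to change.** In 13.5.2 specify beta ~ N+(8, 20^2), truncated at zero as gamma already is. If the software already truncates the slope, say so there. State the dose scale used for d at the same time. Rerun the operating characteristics in 13.5.5 under the stated prior, preferably adding one scenario with lower-dose expansion and DLTs counted through Cycle 3. Check the lowest-dose stopping rule under the restricted prior.

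The cost is one symbol, a rerun of existing simulations and refreshed tables. There are two downsides to declare. The restriction raises the calculated safety of the lowest dose, so the early-stop probability in 13.5.5.7 may fall and must be reported again. It also removes most but not all upward moves: in an ordinal fit with 3 clean patients per level up to 0.15, recoding 2 patients at 0.003 as DLTs still moves the MTD from 0.20 to 0.25 with beta > 0, because the slope flattens.
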